#### 4.1 Inclusion Criteria

All subjects accepted for this trial must:

- Previously received cryotherapy of RCC.
- Be scheduled for contrast-enhanced MRI/CT to monitoring of RCC recurrence as part of their 8, 12, 18, 24, or 36 month CT/MRI follow up.
- Be at least 18 years of age.
- Be medically stable.
- If a female of child-bearing age, must have a negative pregnancy test.
- Have signed Informed Consent to participate in the study.

#### 4.2 Exclusion Criteria

Subjects with any of the following conditions or who have had the following procedures will be excluded from this trial:

- Females who are pregnant or nursing.
- Patients who are medically unstable, patients who are seriously or terminally ill, and patients whose clinical course is unpredictable. For example:
  - Patients on life support or in a critical care unit.
  - Patients with unstable occlusive disease (eg, crescendo angina)
  - Patients with clinically unstable cardiac arrhythmias, such as recurrent ventricular tachycardia.
  - Patients with uncontrolled congestive heart failure (NYHA Class IV)
- Patients with recent cerebral hemorrhage.
- Patients with known sensitivities to albumin, blood, or blood products
- Patients who have undergone surgery within 24 hours prior to the study sonographic examination.
- Patients with known hypersensitivity to perflutren
- Patients with cardiac shunts.
- Patients with congenital heart defects.
- Patients with severe emphysema, pulmonary vasculitis, or a history of pulmonary emboli.
- Patients with respiratory distress syndrome.
- Patients with renal insufficiency such that they cannot get intravenous contrast as part of screening or follow-up.

Subject identification will be maintained with a study specific alphanumeric code including the subject number (01-100).

### 5. MEDICATIONS

Optison will be provided by GE Healthcare, Princeton, NJ.

Optison is a sterile non-pyrogenic suspension of encapsulated perflutren microbubbles [Goldberg et al 2001; Miller & Nanda 2004]. The contrast agent consists of a human serum albumin shell with perflutren core and contains  $5.0 - 8.0 \times 10^8$  microspheres/ ml. The microbubble agent is supplied in a standard-size 3 ml vial and is prepared by manually shaking the vial. Detailed instructions are provided in the Optison Product Insert, found in Appendix B.

Optison will be stored in a secure refrigerator, with only the study investigators and research personnel having access. Unused drug and empty vials will be properly disposed of after reconciling the log of study drug kept at Thomas Jefferson University.

### 5.1 Administration

All contrast injections will be supervised by a board certified physician. Resuscitation equipment and trained personnel will be immediate proximity to the patient during each contrast-enhanced ultrasound exam. Optison will be administered by bolus IV injection through an 18- to 20-gauge angiocatheter placed in a peripheral arm vein, preferably an antecubital vein. Subjects will be instructed not to move their arm during the administration of the contrast agent.

### 5.2 Contraindications

Optison should not be administered to patients with known or suspected hypersensitivity to perflutren, blood, or blood products. The safety of Optison in patients with 1) right-to-left, bi-directional or transient right-to-left cardiac shunts; 2) severe emphysema, pulmonary vasculitis or a history of pulmonary emboli; 3) respiratory distress syndrome has not been studied. Therefore, patients with any of these conditions will be excluded from participation.

### 5.3 Randomization

This is a non-randomized trial; therefore, no randomization procedure is required.

### 5.4 Blinding and Unblinding Methods

This is an open-label trial; therefore, no blinding or unblinding procedures for the trial drug are required.

### 5.5 Storage

Optison vials will be stored in a secure refrigerator, with only the study investigators and research personnel having access. The study research nurse will be responsible for drug suspension and inventory control.

## 6. TRIAL PROCEDURES

### 6.1 Patient Enrollment

Trial Procedures: Subjects eligible for trial enrollment will be identified by the co-investigators, Drs. [name], [name] and [name] from their patient population of subjects under active surveillance for recurrence of a previously cryoablated RCC. A research coordinator will explain the study to the patient. The patient will be given time to consider the risks and benefits of the study and ask questions about participation. The coordinator will review the consent form with the patient and then the patient will be given the form to review. The patient, coordinator, and a study investigator will all sign the consent form. The patient will be given a copy of the signed consent form for their records.

### 6.2 Screening Assessments

Screening assessments will be performed prior to CEUS imaging. Trial participants will have the presence of inclusion criteria and absence of exclusion criteria verified by providing a medical history. A full demographic profile, known drug allergies or intolerances, and a review of the subject's medical/surgical history will be recorded. If the subject is a woman of childbearing age, she will have a urine pregnancy test (the results of which will be made available to the subject prior to study initiation).

### 6.3 Ultrasound Imaging

All contrast injections will be supervised by a board certified physician. Resuscitation equipment and trained personnel will be in immediate proximity to the patient during each CEUS exam. The ultrasound examinations will be performed by a qualified sonographer. Ultrasound exams will take place the morning prior to the patient's 8, 12, 18, 24, or 36 month CT/MRI follow up (scheduled as part of their clinical care) or during their consultation in Jefferson's Urology clinic (for patients who have imaging performed outside Jefferson). Procedures and equipment for this trial will be used in accordance with typical clinical procedures. All trial procedures will be conducted in accordance with Good Clinical Practice. For the ultrasound examination, the patient will be asked to lie in the supine position and a catheter will be placed in a superficial vein (preferably an antecubital vein). Acoustic coupling gel will be applied to the area of interest. A state of the art ultrasound scanner with 2D and 3D curvilinear probes will be used.

A baseline ultrasound grayscale scan will be used to identify the tumor and to evaluate the following criteria: size, shape, and orientation of the lesion; echogenicity compared to surrounding tissue. Standard power Doppler of the lesion will also be performed. When possible, previous MR/CT data will be uploaded onto the scanner in order to perform image fusion for ultrasound guidance during imaging. The distribution of color signals and the overall color content of the tumor will be evaluated by comparing the pattern and amount of color to the normal surrounding tissue. Following baseline scanning, patients will receive a 1 ml intravenous injection of Optison (GE Healthcare, Princeton, NJ) in a peripheral vein followed by renal mass imaging in 2D CHI (a nonlinear contrast imaging package). Ten minutes after the 2D CEUS exam, patients will receive a second bolus injection of Optison followed by 3D CHI (using a curvilinear 3D array). All contrast injections will be supervised by a board certified physician. Resuscitation equipment and trained personnel will be immediate proximity to the patient during each contrast-enhanced ultrasound exam. Digital clips of the exams will be recorded through the contrast agent wash-in and wash-out phases for at least two minutes and stored for later use. The subject will then be monitored for adverse reactions for 30 minutes. If the patient wishes to continue participating in the study, they will be eligible for CEUS exams during their future clinically scheduled follow up exams as long as these take place within the study timeframe.

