Appendix A. Investigator Obligations	
Appendix B. Optison Product Insert	
Appendix C. Case Report Forms	
Appendix D. Thomas Jefferson University IRB Approvals	

## SYNOPSIS

Protocol Title: Two and three dimensional contrast-enhanced ultrasound for screening of renal cell carcinoma recurrence following cryoablation

Trial Objectives: The primary objective of this trial is to:

- Evaluate if contrast-enhanced ultrasound can be used to successfully detect recurrence of renal cell carcinoma following cryoablation therapy when compared to the gold standards of contrast enhanced computed tomography or magnetic resonance imaging.

The secondary aim of this trial is to:

- Establish whether three-dimensional contrast-enhanced ultrasound provides superior screening of renal cell carcinoma recurrence relative to two-dimensional contrast-enhanced ultrasound.

Trial Design: This is an open-label, non-randomized trial that will be conducted at one clinical site. The subject population will be patients scheduled for follow up contrast enhanced computed tomography (CT) or magnetic resonance imaging (MRI) of a previously cryoablated renal cell carcinoma (RCC) through Thomas Jefferson University's Urology clinic. Eligible follow up imaging will include patients being seen for an 8, 12, 18, 24, or 36 month CT/MRI follow up. The study will consist of a single ultrasound exam, although patients will be eligible to re-enroll in multiple studies (for example exams at 8, 12 and 18 months), if these exams fit within the study timeframe.

Ultrasound imaging will be performed using a state of the art ultrasound scanner with two and three dimensional curvilinear transducers. If available, image fusion may also be used from patient's previous MR/CT imaging. Patients will first undergo baseline grayscale B-mode and power Doppler imaging (PDI) of the treated mass. Patients will then receive a bolus 1 ml contrast injection of Optison (GE Healthcare, Princeton, NJ), while being imaged with two-dimensional (2D) dual mode B-mode / coded harmonic imaging. Following a 10 minute wait period to allow for full clearance of Optison, patients will receive a second bolus of contrast agent along with three-dimensional (3D) nonlinear imaging. Tumor vascularity and flow kinetics will be determined using both modes and compared to the patient's corresponding contrast-enhanced MRI or CT exams.

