### 3.1 Trial Duration

Individual participation for the majority of patients will be limited to 1 ultrasound exam during their cryoablation follow up in Thomas Jefferson University's Urology clinic. However, patients will be eligible for serial imaging (for example exams at 8, 12 and 18 months), if these exams fit within the study timeframe. Exams will take place the day of the patient's MRI/CT follow up or during their Urology clinic follow up (in cases where MR/CT imaging is performed outside of Jefferson). The entire ultrasound imaging protocol will require approximately one hour including a 30 min observation period. Patients will be monitored for at least 30 minutes before being discharged.

Subject recruitment is expected to last 22 months (January 2015 – November, 2016). Analysis and publication of results are expected to take an additional 2 months (November 2016– January, 2016). Volunteer Registry Database forms will be submitted to the National Institute of Health's Office of Regulatory Compliance and Quality at the completion of the research study.

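### The fusion rule does not exclude a CEUS exam's own reference MRI/CT, so where that scan already exists, chiefly in patients imaged elsewhere, it could steer CEUS acquisition

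*Combined protocol and SAP*

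**What the plan says.** **Timing.** Section 6.3 sets two pathways. For patients scanned on site, "Ultrasound exams will take place the morning prior to the patient's 8, 12, 18, 24, or 36 month CT/MRI follow up". The alternative is the Urology consultation, "for patients who have imaging performed outside Jefferson". Section 3.1 has the same split in looser words: "Exams will take place the day of the patient's MRI/CT follow up or during their Urology clinic follow up", the clinic option applying "in cases where MR/CT imaging is performed outside of Jefferson". Section 4.1 requires only that the patient "Be scheduled for contrast-enhanced MRI/CT to monitoring of RCC recurrence as part of their 8, 12, 18, 24, or 36 month CT/MRI follow up".

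**Fusion.** Section 6.3, and the procedures text of the synopsis, state that when possible "previous MR/CT data will be uploaded onto the scanner in order to perform image fusion for ultrasound guidance during imaging". The design text of the synopsis is permissive: "If available, image fusion may also be used from patient's previous MR/CT imaging". Section 3 is also permissive, and gives the purpose as help with scanning and finding the lesion.

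**Reference standard and reading.** Sections 6.5 and 7.2 calculate sensitivity, specificity, accuracy and predictive values against contrast-enhanced CT or MRI, and against pathology if the patient is retreated. Two radiologists, described as blinded, review the CEUS and MRI/CT exams independently. Section 5.4 deals with blinding only for the trial drug. Section 6.3 has clips stored for later use.

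**The concern.** An accuracy study needs the index test to be obtained without knowledge of the reference result. Here the operator may have the reference images on the scanner while deciding where to point the probe. Recurrence is initially defined by enhancement inside the ablation cavity, so knowing where the reference scan enhanced could decide whether a small focus is captured at all. The readers then interpret clips whose content was chosen with that knowledge, and blinding them cannot restore independence.

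The primary objective is at stake, since it is detection of recurrence judged against CT/MRI. The quantitative perfusion parameters in Section 7.2 come from the same acquisitions and are correlated with the same scan. Enrolling more patients would not remove the problem. If dates and fusion use are not recorded, it cannot be measured afterwards either.

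**Working it through.** Most of this check compares the text of different sections. The arithmetic gives scale only.

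**1. Can the reference scan exist when CEUS is done?**
- On site, Section 6.3: no, because CEUS comes on the morning before the scan.
- On site, Section 3.1: not settled. It puts both on the same day without an order.
- Imaged elsewhere, Sections 3.1 and 6.3: not settled. They give a place, the consultation, but no order relative to the outside scan. A scan done before the consultation is the natural reading, but it is not stated.
- Section 4.1: being scheduled for a scan fits either order.

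The reference scan may therefore already exist, mainly in patients imaged elsewhere.

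**2. Does the fusion rule keep it out?** No. The rule has no date limit, no definition of *previous*, and no exclusion of the paired scan.

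**3. Does another safeguard keep it out?** None is written. The sonographer is not blinded to MR/CT. What the readers are blinded to is not stated. There is no rule on whether a fused view is kept in stored clips.

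**4. The plan's own precision figure.** Section 7.2.1 assumes 100 patients and 5% recurrence, so 95 are non-recurrent. With specificity 0.90, x = 0.90 × 95 = 85.5. The two-sided 90% Clopper-Pearson limits are:
- lower: 5th percentile of Beta(85.5, 10.5) = 0.834
- upper: 95th percentile of Beta(86.5, 9.5) = 0.946
- width: 0.946 − 0.834 = 0.112

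This matches the plan's table, which the present point does not affect.

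**5. Sensitivity.** Expected recurrences are 100 × 0.05 = 5. One recurrence changed from missed to detected moves sensitivity by 1/5 = 20 points, for example from 4/5 (95% exact interval 0.284 to 0.995) to 5/5 (0.478 to 1). This happens only if at least one recurrent case was fused with its own reference scan and would otherwise have been missed.

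**6. Specificity, illustration only.** Let f be the share of exams fused with their own reference scan, and g the share of would-be false positives that this removes. The documents give neither, so both are assumed. At a true specificity of 0.90:

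apparent specificity = 0.90 + 0.10 × f × g

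- f = 0.10, g = 0.25: 0.90 + 0.0025 = 0.9025
- f = 0.25, g = 1: 0.90 + 0.025 = 0.925
- f = 0.50, g = 1: 0.90 + 0.05 = 0.950

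Over f from 0.10 to 0.50 and g from 0.25 to 1, the shift is 0.25 to 5 points, against a planned interval about 11 points wide. Guidance alone does not erase enhancement that CEUS shows in the cavity. The higher values of g would in effect need the readers to see the reference scan.

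**The case against.** The strongest reply is that the plan means earlier scans. The synopsis uses *previous* for the imaging to be fused but *corresponding* for the MRI/CT that CEUS is compared with, which suggests different scans. For on-site patients under Section 6.3, *previous* can only mean an earlier scan. Sections 1 and 1.1 place an initial scan at 3 to 4 months, before every eligible visit, so an earlier scan should normally be available. This is a fair reading and may be what was intended. It is not written as a rule, though, and a site that fused the paired scan would not breach the text.

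Several stronger conclusions are tempting, and the documents do not support them:

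- *The outside scan has always been done by the CEUS visit.* This is an inference; no section gives the order.
- *Readers see the reference scan through fused views in the clips.* This is possible but not described. Fusion is for guidance, the 2D contrast display in the synopsis has no MR/CT view, and the reading is described as blinded and independent.
- *Specificity is inflated by about 1 to 7.5 points.* That range follows from assuming 10% to 30% of exams affected and true specificity of 0.90 to 0.75 (0.10 × 0.10 = 0.010; 0.30 × 0.25 = 0.075). The shares have no basis in the documents, and the formula removes every false positive in affected exams, which steering the probe does not do.
- *Patients imaged elsewhere differ systematically from on-site patients.* No section compares them.

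It is also true that this is a pilot meant to inform a fully powered study. That limits the consequences, but its accuracy estimates are what the later study would build on.

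**Conclusion.** The concern holds as a gap in the plan that permits bias, not as proof that bias will occur. The plan allows CEUS acquisition to be guided by its own reference standard wherever the reference scan comes first. That is most plausible for patients imaged elsewhere, and Section 3.1 leaves it open for others.

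The direction is toward inflated agreement with MRI/CT, mainly through sensitivity, where one affected recurrence out of about 5 is worth 20 points. That figure rests on the plan's assumptions of 100 patients and 5% recurrence. The expected size cannot be derived, because the documents give neither the share imaged elsewhere nor the share that would be fused with the paired scan. The specificity range above shows scale under assumed inputs and is not an estimate.

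The change is worth making before imaging starts, because a steered acquisition cannot be corrected later.

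**What to change.** - **Sections 6.3 and 3, and the synopsis:** state that fusion uses only MR/CT that predates the paired reference exam (pre-ablation or an earlier follow-up time point), and never the scan that serves as reference for that CEUS exam. Keep any MR/CT panes or overlays out of the clips given to readers.
- **Section 6.5:** state what the sonographer and the readers are blinded to.
- **Sections 3.1 and 6.3:** reconcile the two descriptions of timing.
- **Case report form:** record whether fusion was used, the date of the fused scan, and the order of and interval between CEUS and MRI/CT.
- **Section 7.2:** repeat the accuracy analysis excluding any exam fused with its paired reference scan, or restricted to exams where CEUS came first. Restricting to same-day pairs is not enough: it does not fix the order, and it drops unaffected exams.

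The cost is older guidance images, or no fusion, in a few patients, a few form fields, some clip preparation and one extra analysis. Fusion for locating the lesion is kept, and the sample size does not change.

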#### 6.4 Safety Monitoring

Patients will be monitored for AEs during and 30 minutes after contrast administration. All other procedures will be performed according to standard of care. No further patient monitoring is required as side effects of Optison are acute in nature and no renal toxicity has been reported (See Table 1, section 2.1).

#### 6.5 Efficacy Assessments

Both 2D and 3D CEUS exams and the clinically-indicated contrast-enhanced MRI/CT exam will be independent and randomly reviewed by two blinded radiologists with experience in both CEUS and body imaging. Readers will evaluate the presence of signal enhancement within the mass, signal distribution and heterogeneity, signal intensity relative to the normal renal parenchyma, and contrast agent wash-in and wash-out kinetics relative to the surrounding parenchyma. The readers will also be asked to evaluate if CEUS findings indicate RCC recurrence. Recurrence will initially be defined as the presence of contrast enhancement within the ablation cavity. Finally, following a one month wait period and randomization, readers will again review cases in order to calculate intra-reader variability. Both qualitative and quantitative findings will be obtained for the ultrasound study. Sensitivity, specificity,

accuracy, positive predictive value, and negative predictive value will be calculated for the contrast-enhanced ultrasound exam using both the standard of care contrast-enhanced CT or MRI, and pathology (if retreated) as the reference standards. The dichotomous parameter needed for these calculations will be derived by ascertaining whether blinded radiologists would recommend further treatment or not based on the degree of residual blood flow observed during the CEUS study. Correlations between these assessments and both contrast-enhanced MRI or CT findings will be compared using the Fisher exact test. Inter- and intra-observer variability will also be calculated. Quantitative parameters of mass vascularity, perfusion, and contrast fill time will be computed relative to the surrounding renal parenchyma and again correlated to the clinical standard. Finally, the patient's billed amount for their contrast-enhanced MRI/CT exam (cost of exam prior to insurance reimbursements) will be recorded and compared to the cost of a real ultrasound exam and one vial of ultrasound contrast agent to compare potential cost savings to the patient. Quantitative parameters will be compared between recurrent and disease free groups using a Student's t-test.

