### 7.2 Statistical Analyses

Qualitative findings will be generated from Radiologist interpretations of exams. Both 2D and 3D CEUS exams and the clinically-indicated contrast-enhanced MRI/CT exam will be independent and randomly

reviewed by two blinded radiologists with experience in both CEUS and body imaging. Readers will evaluate the presence of signal enhancement within the mass, signal distribution and heterogeneity, signal intensity relative to the normal renal parenchyma, and contrast agent wash-in and wash-out kinetics relative to the surrounding parenchyma. The readers will also be asked to evaluate if CEUS findings indicate RCC recurrence. This parameter will be based off of each reader's first read. In the event of discordant readings during this analysis, recurrence will be decided by consensus by the two readers. Finally, following a one month wait period and randomization, readers will again review cases in order to calculate intra-reader variability.

Quantitative findings will be generated by calculating of mass vascularity, perfusion, and contrast fill time. This will be done using a commercial contrast quantification package, which fits wash-in and wash-out curves to signal intensity as a function of time to quantify key parameters. Contrast parameters in the area of the previously treated mass will be computed relative to the surrounding renal parenchyma and again correlated to the clinical standard. Finally, the patient's billed amount for their contrast-enhanced MRI/CT exam (cost of exam prior to insurance reimbursements) will be recorded and compared to the cost of a real ultrasound exam and one vial of ultrasound contrast agent to compare potential cost savings to the patient.

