Data will first be analyzed on a per case basis (treating each case as an independent data point). However, analysis may also be performed on a patient by patient basis if a large number of enrolled patients undergo serial imaging (potentially required to ensure adequate enrollment). Sensitivity, specificity, accuracy, positive predictive value, and negative predictive value will be calculated for the qualitative data using both the standard of care contrast-enhanced CT or MRI, and pathology (if retreated) as the reference standard. The dichotomous parameter needed for these calculations will be derived by ascertaining whether blinded radiologists would recommend further treatment or not based on the degree of residual blood flow observed during the contrast-enhanced ultrasound. Correlations between these findings and both contrast-enhanced MRI or CT findings will be compared using the Fisher exact test. Inter-rater variability will be calculated using each reader's first set of reads, while intra-rater variability will be calculated by comparing each reader's initial and 1 month analysis. Intra-rater and inter-rater variability will be calculated using a Shrout and Fleiss Interclass Correlation [Shrout and Fleiss 1979]. Quantitative parameters will be compared between groups using a Student's t-test.

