### 7.2.1 Sample Size Calculation

We hope to enroll up to 100 patients within 22 months as part of this study. This should be achievable,

given that our Urology clinic sees approximately 200 cryoablation follow up patients annually. As this is a pilot feasibility study it is difficult to estimate statistical power *a priori*. However, a power analysis was run in PASS12 (NCSS LLC, Kaysville, UT) to estimate the size of the confidence interval when estimating the test's overall level of specificity. A two sided confidence interval of one proportion was simulated using a Clopper-Pearson exact solution, assuming 100 patients and a total study recurrence rate of 5%. The relationship between the confidence level and 95% confidence interval and confidence interval width is shown below.

Confidence Level	Size (N)	Target Width	Actual Width	Proportion (P)	Lower Limit	Upper Limit	Width if P = 0.5
0.800	95		0.089	0.900	0.849	0.938	0.141
0.850	95		0.099	0.900	0.842	0.941	0.157
0.900	95		0.112	0.900	0.834	0.946	0.177
0.950	95		0.131	0.900	0.821	0.952	0.209

Thus, we expect 100 patients will enable us to estimate the specificity of the test to within 11% with 90% confidence. While multiple time points of the same patients cannot strictly be treated as independent samples (required to achieve adequate sample size within the two year window), data will also be analyzed on a per patient basis. Additionally, data from this study will also be used for future grant submissions to run a fully powered study in which conclusive hypotheses comparing 2D and 3D, as well as quantifiable parameters can be answered.

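### Should the Student's t-test on the quantitative CEUS parameters be replaced by a Welch test because only about 5 of 100 exams will be recurrences?

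*Combined protocol and SAP*

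**What the plan says.** Section 7.2 names the outcomes: "Quantitative findings will be generated by calculating of mass vascularity, perfusion, and contrast fill time". Section 6.5 adds that they "will be computed relative to the surrounding renal parenchyma and again correlated to the clinical standard". Section 1.2 identifies that standard as contrast-enhanced MRI or CT.

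For the group comparison, section 6.5 states "Quantitative parameters will be compared between recurrent and disease free groups using a Student's t-test". Section 7.2 repeats it in shorter form: "Quantitative parameters will be compared between groups using a Student's t-test". Neither section mentions an unequal-variance form, a transformation, a rank-based alternative, group SDs or a confidence interval.

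The group sizes follow from section 7.2.1, which works out its precision table "assuming 100 patients and a total study recurrence rate of 5" per cent. The unit is the exam: "Data will first be analyzed on a per case basis (treating each case as an independent data point").

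Section 7.2.1 also limits what the study claims. It says "As this is a pilot feasibility study it is difficult to estimate statistical power" in advance, and it looks to a later, fully powered study in which "conclusive hypotheses comparing 2D and 3D, as well as quantifiable parameters can be answered".

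**The concern.** In its standard form, Student's t-test pools the two variances, weighting each by its degrees of freedom. With 5 v 95, the pooled variance is almost entirely that of the disease-free group. The uncertainty of the difference in means, however, comes almost entirely from the 5 recurrences. If recurrent exams vary more than disease-free exams, the pooled standard error is too small and the p-value too optimistic. If they vary less, the test is too conservative.

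Greater spread among recurrences is plausible for vascularity and perfusion, because a well-ablated cavity should show little or no enhancement. For fill time the direction is unclear. At stake are the p-values of this one comparison and any planning values that the later study takes from it.

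**Working it through.** **1. The plan's own figure.** Section 7.2.1 gives no calculation for the t-test. Its only sample-size figure is the Clopper-Pearson width for specificity with N = 95 and P = 0.90. With x = 0.90 × 95 = 85.5, beta quantiles give 0.834 to 0.946 at 90% confidence, a width of 0.1115 against the printed 0.112. The other three rows also reproduce. This confirms the split: 100 × 5% = 5 recurrent and 95 disease-free.

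**2. Where the variance comes from.** Let r be the SD of recurrent exams divided by the SD of disease-free exams. The documents give no SDs, so r is assumed.

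- Recurrent share of the pooled variance: 4r²/(4r² + 94). This is 4/98 = 4%, 16/110 = 15% and 36/130 = 28% at r = 1, 2 and 3.
- Recurrent share of the true variance of the difference: (r²/5)/(r²/5 + 1/95). This is 95%, 98.7% and 99.4% at r = 1, 2 and 3.
- True SE over pooled SE: √(r²/5 + 1/95) / √{[(4r² + 94)/98](1/5 + 1/95)}. At r = 2 this is √0.8105/√(1.1224 × 0.2105) = 1.85.

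**3. False-positive rate with normal data.** Simulation, 5 v 95, equal means; the two-sided 5% level is assumed.

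| r | True SE / pooled SE | Student | Welch |
|---|---|---|---|
| 0.5 | 0.54 | 0.04% | 5.9% |
| 1 | 1.00 | 5.0% | 5.6% |
| 1.25 | 1.22 | 10.9% | 5.5% |
| 1.5 | 1.44 | 17.3% | 5.4% |
| 2 | 1.85 | 28.6% | 5.2% |
| 3 | 2.55 | 44.0% | 5.1% |

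The sensitivity is therefore real for roughly normal data, and it runs in both directions.

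**4. What Welch costs when the SDs are equal.** Median 95% interval width rises from 1.81 to 2.24 SD (2.24/1.81 = 1.24). Power falls from 58% to 41% for a 1 SD difference, and from 80% to 60% for 1.3 SD.

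**5. Welch in skewed data.** Relative vascularity or perfusion in an ablated cavity is likely to sit near zero with a right tail. The distributions below are assumed.

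- *Both groups from one distribution (no difference at all).* Exponential: Student about 5%, Welch 12%. Log-normal with log-SD 1: Student about 5%, Welch 17%.
- *Gamma data, equal means, unequal SDs* (disease-free mean and SD 0.10, recurrent mean 0.10). At r = 1.5, 2 and 3, Student rejects 12%, 20% and 37%; Welch rejects 19%, 26% and 41%.
- *Gamma data, recurrent mean 0.2, 0.3 or 0.5, r from 1.5 to 3.* Welch intervals cover 81% to 94% and pooled intervals 55% to 84%. Power at mean 0.3 is 77% to 96% for Student and 11% to 66% for Welch. At mean 0.2 it is 42% to 51% and 6% to 13%.

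**6. Fewer recurrences than planned.** For a Binomial(100, 0.05) count, P(2 or fewer) = 12% and P(0 or 1) = 3.7%. With 2 recurrences and normal data, Welch rejects 8% to 13% over r from 0.25 to 3. With fewer than 2 it cannot be computed.

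**The case for a change.** The best case for a change is that the SDs are unknown, so a method that relies on their equality at 5 v 95 should not be the only one planned. A 25% excess in the recurrent SD already doubles the error rate (5.0% to 10.9%). When the means truly differ, the Welch interval is closer to 95% coverage than the pooled interval in all nine gamma settings. Part of Student's apparent power in those settings comes from an understated standard error. The later study will need group SDs, which the plan does not promise, and the edit would take two sentences.

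Much of this stands. If the aim is an interval for a real difference, the unequal-variance form is usually the better one, and group SDs should be reported. It does not show that the planned test is an error. The harm depends on a ratio that could fall on either side of 1. Exams on disease-free patients that look recurrent would widen the larger group and pull the ratio down. When the two groups do not differ in any way, Student holds its level even in skewed data and Welch does not. With about 5 recurrences, competent statisticians would differ over Welch, a rank test, a permutation test or a transformation. Listing n, mean and SD by group is routine in reporting and needs no instruction in the plan.

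Serial exams of one patient are a separate matter. Neither test handles them, and section 7.2.1 already acknowledges the dependence.

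**Conclusion.** No change to the plan is needed. The pooled t-test is sensitive to unequal spread at about 5 v 95: its false-positive rate runs from 0.04% to 44% as the SD ratio goes from 0.5 to 3. Those figures assume normal data, equal means, a two-sided 5% level and SD ratios that the documents do not supply. No wrong result is shown.

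Replacing the test with Welch would exchange one weakness for another, with lower power and over-rejection in skewed data, in a comparison that rests on about 5 recurrences whichever method is used. The consequence is confined to a secondary, exploratory analysis with no power claim or decision rule attached. The diagnostic accuracy measures are untouched.

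An analyst would sensibly report each parameter by group, show the individual recurrent values, and place an unequal-variance interval and a rank or permutation check beside the planned test. That is good practice within the plan as written.
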